**Definition of secondary outcomes/endpoints:**

1. Incidence of adverse events of the combination defined by CTCAE 4.1 criteria.  
Toxicity will be any drug related Grade 3 or 4 toxicity.
2. Response duration to the combination recorded from start of treatment to progression
3. Overall survival measured from start of treatment to death or last follow up

**Sample size justification and study design:** The study sample size was determined using Minimax Simon's two-stage design (Simon, 1989. The null hypothesis that the true response rate is 0.3 will be tested against a one-sided alternative that the true response rate is 0.5. In the first stage, 12 patients will be accrued. If there are 3 or fewer responses, the study will be stopped. Otherwise, 16 additional patients will be accrued for a total of 28. The null hypothesis will be

rejected if 11 or more responses are observed in 28 patients. This design yields a type I error rate of 0.1 and a power of 0.8 when the true response rate is 0.5.

**Analysis plan:** Descriptive statistics will be used for the primary endpoint and secondary endpoints 1,2, and 3. Overall survival will be estimated with Kaplan Meier method and will be compared to the survival of a historical cohort of MDS patients treated at our institution with single agent Azacitidine between 2006-2012 using a one-sample log rank test. A Cochran-Mantel-Haenszel test will be used to test for differences in response rate by mutational status controlling for treatment. Unadjusted and adjusted logistic regression models were used to predict response to therapy. Models will be adjusted for covariates including age, sex, and other prognostic factors. The odds ratio (OR) and 95% confidence intervals (CI) will be estimated for the risk group (mutated) and compared with the reference group (WT).

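### The final Simon boundary is off by one: rejecting at 11 or more of 28 gives a type I error of 0.169, not the stated 0.1

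*Combined protocol and SAP*

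**What the plan says.** The design is set out in Section 14.0, in the paragraph on sample size justification and study design. "The study sample size was determined using Minimax Simon's two-stage design". "The null hypothesis that the true response rate is 0.3" is "tested against a one-sided alternative that the true response rate is 0.5".

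- Stage 1: "In the first stage, 12 patients will be accrued". "If there are 3 or fewer responses, the study will be stopped".
- Stage 2: "Otherwise, 16 additional patients will be accrued for a total of 28".
- Final rule: the null hypothesis is "rejected if 11 or more responses are observed in 28 patients".
- Claimed properties: "This design yields a type I error rate of 0.1 and a power of 0.8 when the true response rate is 0.5".

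The Protocol Summary and Section 3.1 repeat the total of 28 but give no boundary. The amendment summaries in Appendix VIII list no change to this rule.

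**The concern.** In Simon's notation a two-stage design is given as r1/n1 and r/n, and both r values are the largest counts at which the regimen is *not* taken forward. Stop at r1 or fewer; fail to reject at r or fewer; reject only above r. The plan applies this correctly at stage 1, where 3 or fewer stops the trial. At the final stage the plan's number appears as the smallest count that rejects. If 11 is Simon's r, the written threshold is one response too low.

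This is the only rule for declaring success on the primary endpoint. If it is one too low, the chance of declaring success for a regimen no better than the null rate is well above what the plan tells its readers. A final count of exactly 11 would then be a success under the written cut-off and a failure under the stated error rate. If that is noticed only once the data are known, either choice of boundary can be challenged as post hoc.

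**Working it through.** **Inputs** (all from Section 14.0): p0 = 0.3, p1 = 0.5, n1 = 12, stop if X1 ≤ 3, 16 further patients, n = 28, final cut-off k = 11.

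**Formula.** With X1 the stage 1 responses and X2 the stage 2 responses, the probability of rejecting at true rate p is

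P(reject | p) = Σ (x = 4 to 12) P[Bin(12, p) = x] × P[Bin(16, p) ≥ k − x].

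This is the type I error at p = 0.3 and the power at p = 0.5.

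**Type I error (p = 0.3)**

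| Stage 1 responses x | P(X1 = x) | P(X2 ≥ 11 − x) | Product, k = 11 | P(X2 ≥ 12 − x) | Product, k = 12 |
|---|---|---|---|---|---|
| 4 | 0.2311 | 0.1753 | 0.0405 | 0.0744 | 0.0172 |
| 5 | 0.1585 | 0.3402 | 0.0539 | 0.1753 | 0.0278 |
| 6 | 0.0792 | 0.5501 | 0.0436 | 0.3402 | 0.0270 |
| 7 | 0.0291 | 0.7541 | 0.0220 | 0.5501 | 0.0160 |
| 8 to 12 | | | 0.0087 | | 0.0074 |
| **Total** | | | **0.1687** | | **0.0954** |

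**Both properties, by final cut-off** (the same sum at p = 0.5 gives the power)

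| Reject if | Type I error (p = 0.3) | Power (p = 0.5) |
|---|---|---|
| 10 or more | 0.2611 | 0.9040 |
| **11 or more (as written)** | **0.1687** | **0.8682** |
| **12 or more** | **0.0954** | **0.8020** |
| 13 or more | 0.0471 | 0.7002 |

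The plan's stated 0.1 and 0.8 are not reproduced at 11. They are reproduced at 12, and at no other cut-off in the table.

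**Where the plan's numbers come from.** An exhaustive search over two-stage designs with p0 = 0.3, p1 = 0.5, type I error at most 0.10 and power at least 0.80 gives a smallest total of 28. Among the designs of that size, the one with the lowest expected sample size under the null is n1 = 12, r1 = 3, n = 28, r = 11. Its probability of stopping at stage 1 under p = 0.3 is P[Bin(12, 0.3) ≤ 3] = 0.4925, so the expected size is 12 + (1 − 0.4925) × 16 = 20.1. The plan's stage sizes and stage 1 boundary are exactly these. Here r = 11 means that more than 11 responses, that is 12 or more, are needed to reject.

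**Other readings of the text, with the cut-off held at 11 of 28**

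- Stage 1 stop treated as non-binding (single-stage test of 28): type I error 0.1913, power 0.9075.
- Stage 1 boundary of 2: 0.1865 and 0.9004.
- Stage 1 boundary of 4: 0.1281 and 0.7749.
- Stage 1 boundary of 5: 0.0742 and 0.6018.
- Every stage 1 size from 1 to 27 with every stage 1 boundary: none gives type I error at most 0.10 together with power at least 0.80.

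**Size of the discrepancy.** The two cut-offs part only when the trial passes stage 1 and ends at exactly 11 responses:

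- p = 0.3: 0.1687 − 0.0954 = 0.0733
- p = 0.5: 0.8682 − 0.8020 = 0.0662 (0.0663 before rounding)

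Relative to the stated 0.10, the type I error is 0.1687 / 0.10 = 1.69 times as large. Relative to the 0.0954 of the matching design, it is 0.1687 / 0.0954 = 1.77 times. In plain terms, 1 / 0.1687 = 5.9, so about one false success in six.

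**The case against.** No reading rescues a type I error of 0.1 with a cut-off of 11, but several points limit what the error does.

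First, its reach is narrow. Every final count other than 11 leads to the same conclusion under either cut-off. The stage 1 rule is correct, and accrual and patient numbers are untouched. This stands.

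Second, the trial is framed partly as estimation. The primary objective in Section 2.1 is to estimate the response rate, and the analysis plan in Section 14.0 calls for descriptive statistics on the primary endpoint. A reader could say the test carries little weight. This softens the consequence but does not remove the error, because the same section states a null hypothesis, a rejection rule and the rule's error rates.

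Third, the cause is inferred. The documents do not show the output of the design software, so the misreading of r is probable, not proven. That stands too. The mismatch between the rule and its stated properties does not depend on the explanation.

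**Conclusion.** The concern holds. The written rule has a type I error of 0.169 and power of 0.868, against the stated 0.1 and 0.8. Rounding does not explain either gap. The same design with rejection at 12 or more has 0.095 and 0.802 and is the minimax design for the stated targets. The practical effect is confined to a result of exactly 11 of 28 (11/28 = 39.3%), which has probability 0.073 at a true rate of 0.3 and 0.066 at 0.5.

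The figures assume independent binomial responses with a common rate, exactly 12 and 28 patients counted at the two looks, and a binding stage 1 stop. If the stop is not enforced, the type I error at a cut-off of 11 rises to 0.191.

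**What to change.** In Section 14.0, change the final rule so that the null hypothesis is rejected at 12 or more responses among 28 patients, and give the exact properties: type I error 0.095 and power 0.802. If the sponsor prefers to keep 11, leave the rule and restate the properties as type I error 0.169 and power 0.868. Make the choice before the final response count is known.

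The cost is one number and one sentence. Stage 1, the total of 28 and the conduct of the trial do not change.

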Secondary Objective(s)	
Secondary Endpoint(s)
 
 
1. The safety profile of the combination in the targeted patient population
 
2. Response duration
 
3. Overall survival of the treated population (compared to matched historical cohort of patients treated with single agent Azacitidine)
 
4. The identification of biomarkers that predict response to
 

	the combination
Correlative Objective(s)	Correlative Endpoint(s) Identify gnomonic biomarkers for response. Evaluate methylation profile and after treatment to determine its relation with response.
Sample Size	28
Disease sites/Conditions	Myelodysplastic Syndromes (MDS), MDS/MPN syndromes, and AML
Interventions	Azacitidine 75 mg/m  , SC / IV day (1-7) every 28 days cycle Ascorbic acid 1 g PO every day (daily) for every 28 days cycle

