Treatment with AZA and DAC improves cyopenias and prolongs survival in patients with MDS, though only 30-40% of patients respond to therapy. Azacitidine was approved in USA based on phase III clinical trial that compared azacitidine to best supportive care. Overall response rate to azacitidine was 34% with significant delay in AML transformation but no overall survival benefit. In a phase III clinical trial conducted in Europe, azacitidine was compared to conventional care arm that included best supportive care, low dose cytarabine, and intensive chemotherapy. The median OS for patients treated with azacitidine was 24.5 months compared to 15 months for patients treated with best supportive care (HR .58, p = .00001).

Studies have shown that MDS patients with *TET2* mutations have a higher response rate to AZA. In a study of 82 patients with MDS and oligoblastic AML (20-30% BM blasts) treated with AZA, *TET2* mutations were found in 15% of the patients. Patients with *TET2* mutations had a higher response to AZA compared to wild type patients (82% vs 45%, p = 0.04, respectively). In a larger retrospective study, samples from 213 patients with MDS were sequenced prior to their treatment with hypomethylating agents (HMAs) for the presence of 40 recurrent gene mutations. *TET2* mutations with variant allelic frequency (VAF) >10% were associated with a significantly higher overall response rate (ORR) compared with WT (60% vs. 43%; OR, 1.99;

95%CI, 1.05-3.80,  $P=0.036$ ). Further, mice with transplanted TET2-null hematopoietic cells exhibit decrease in white blood counts when they are treated with AZA compared to vehicle.

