### **2.2      Secondary Objective(s)**

To evaluate the following:

1. The safety profile of the combination of azacitidine and ascorbic acid in the targeted patient population.
2. The response duration for study patients.
3. The overall survival of the treated population (compared to matched historical cohort of patients treated with single agent Azacitidine)
4. The identification of genomic biomarkers that may predict response to the combination treatment.

5. Evaluation of changes in methylation prior and during therapy

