#### **4.1 Subject Selection**

#### **4.2 Inclusion Criteria**

Subjects must meet all of the following inclusion criteria to be eligible for enrollment:

4.2.1 Patients must have a confirmed *TET2* mutations identified by next generation targeted deep sequencing.

4.2.2 Patients must have MDS, or MDS/MPN overlap defined by 2016 WHO criteria. Both newly diagnosed or previously treated MDS or MDS/MPN patients are eligible as long as the patient has never received prior treatment with azacitidine or decitabine.

4.2.3 Patients with Leukemic/blast phase transformation MPN.

4.2.4 Patient with AML according to 2016 WHO criteria (excluding APL [AML-M3]).

4.2.4.1 Newly diagnosed patients who are ineligible or declined to receive intensive chemotherapy after discussion of risks and benefits of that approach or patients with primary refractory/relapsed AML.

4.2.4.2 Patients with active central nervous system (CNS) leukemia eligible at the discretion of treating physician.

4.2.4.3 Relapse/Refractory is defined as at least 1 course of treatment for AML excluding any patients treated with azacitidine or decitabine.

4.2.4.3.1 Patients should be off any prior treatment or line of therapy for 2 weeks prior to start study with the exception of hydrea (Hydroxyurea).

4.2.5 Prior therapy with hydroxyurea, biological or targeted therapy (e.g. flt3 inhibitors, other kinase inhibitors) or hematopoietic growth factors is allowed.

4.2.6 Age  $\geq 18$  years.

4.2.7 ECOG performance status  $\leq 3$ .

4.2.8 Patients must have normal organ and marrow function as defined at the discretion of the treating physician and PI.

- 4.2.9 Women of childbearing potential must have a negative serum or urine pregnancy test within 10-14 days prior to enrollment.
- 4.2.10 Patients must have the ability to understand and the willingness to sign a written informed consent document.
- 4.2.11 Patient must be willing to comply with all aspects of the protocol including completing the drug diary.
- 4.2.12 Patient must discontinue any and all use of multivitamin and/or vitamin c medication 24 hours before first dose of Ascorbic Acid.

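### Overall survival is promised against a matched azacitidine cohort, but the analysis plan tests it against 2006-2012 MDS patients with no matching stated, in a TET2-selected trial that also enrols AML and blast-phase MPN

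*Combined protocol and SAP*

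**What the plan says.** The secondary objective in Section 2.2 reads "The overall survival of the treated population (compared to matched historical cohort of patients treated with single agent Azacitidine". The Protocol Summary says the same: "Overall survival of the treated population (compared to matched historical cohort of patients treated with single agent Azacitidine".

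The analysis plan in Section 14.0 is the only place that names the cohort and the test. After estimating OS by Kaplan-Meier, it compares OS with the survival of a "historical cohort of MDS patients treated at our institution with single agent Azacitidine between 2006-2012 using a one-sample log rank test". It gives no matching variables or method, no TET2 status or size for the cohort, and no alpha or sidedness for this test. The sentence before it lists OS (secondary endpoint 3) among the endpoints to be summarised with descriptive statistics.

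The inclusion criteria in Section 4.2 define who is treated:
- 4.2.1 requires confirmed TET2 "mutations identified by next generation targeted deep sequencing".
- 4.2.2: "Patients must have MDS, or MDS/MPN overlap defined by 2016 WHO criteria".
- 4.2.3 also admits "Patients with Leukemic/blast phase transformation MPN".
- 4.2.4 admits AML other than APL; 4.2.4.1 includes "patients with primary refractory/relapsed AML".

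**The concern.** The objective and the analysis plan do not describe the same comparison. The objective covers everyone treated and promises matching. The plan supplies an MDS reference and is silent on matching. Read literally, AML and blast-phase MPN patients would have their expected deaths computed from MDS survival, and a wholly TET2-mutated group would be set against a cohort whose TET2 status is not given. The cohort was treated in 2006-2012, while the amendments in Appendix VIII date from 2017 and 2018.

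A p-value from that test would mix any effect of adding ascorbic acid with diagnosis mix, TET2 selection and calendar period. Since the reference is not pinned down, it could also be settled after the trial data are known. What is at stake is how the OS result can be interpreted. The Simon two-stage decision on response does not use it.

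**Working it through.** **No figure to reproduce.** The documents give no sample size, alpha, power or reference curve for the OS test. The textual comparison above carries the point. The calculation below only shows how large the distortion could be, and in which direction.

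**Inputs from the documents**
- n = 28 (Section 3.1).
- Follow-up: six 28-day cycles plus one year after end of treatment (Sections 3.2 and 11.2, note K): (6 × 28 + 365)/30.44 = 17.5 months. Actual follow-up will vary by patient.
- Reference median 24.5 months. Section 1.1 reports, for an external trial: "The median OS for patients treated with azacitidine was 24.5 months". The institutional cohort's own median is not given.

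**Assumptions not in the documents:** exponential survival; AML share 25% (7 of 28); AML medians of 6 to 20 months; a hazard ratio (HR) of 0.7 from TET2 selection or calendar period; two-sided 0.05, or one-sided 0.05 for benefit.

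**Formulas.** The one-sample log-rank statistic is Z = (O − E)/√E. With F = 17.5 months, reference hazard λ₀ = ln 2/24.5 and hazard λ in a group of size n:
- expected O = n(1 − exp(−λF))
- expected E = O × λ₀/λ

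Reference patients: 1 − exp(−17.5 × ln 2/24.5) = 0.39 deaths per patient, so O = E = 28 × 0.39 = 10.9.

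Example, 7 AML patients with a median of 10 months: O = 7 × 0.703 = 4.92 and E = 4.92 × 10/24.5 = 2.01. Adding 21 MDS patients (O = E = 8.20) gives O = 13.1 and E = 10.2, so Z is shifted by 2.9/√10.2 = +0.91.

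**Results with no treatment effect** (rates simulated, 100,000 or more replicates)

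| Trial patients | O | E | Shift in Z | Rate |
|---|---|---|---|---|
| 28 MDS | 10.9 | 10.9 | 0 | false worse 3.6% two-sided; false better 3.9% one-sided |
| 21 MDS + 7 AML, median 20 months | 11.4 | 10.8 | +0.18 | false worse 5% two-sided |
| same, median 16 months | 11.9 | 10.6 | +0.40 | false worse 8% two-sided |
| same, median 10 months | 13.1 | 10.2 | +0.91 | false worse 17% two-sided |
| same, median 6 months | 14.3 | 9.7 | +1.47 | false worse 32% two-sided |
| 28 MDS, HR 0.7 | 8.2 | 11.7 | −1.03 | false better 24% one-sided |
| 21 MDS, HR 0.7 | 6.15 | 8.8 | −0.89 | false better 21% one-sided |
| 14 MDS, HR 0.7 | 4.1 | 5.9 | −0.73 | false better 17% one-sided |
| 21 MDS, HR 0.7, + 7 AML, median 10 months | 11.1 | 10.8 | +0.08 | false better 2.4% one-sided |

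**Power for a true HR of 0.6 in all patients (one-sided 0.05).** It is 39% if all 28 have MDS. Pooling 21 MDS with 7 AML patients gives 14% or 5% at AML medians of 10 or 6 months, and about 28-34% at 16-20 months. Testing the 21 MDS patients alone gives 33%.

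**The case against.** **OS is descriptive and secondary.** This is true and limits the weight of the point: no decision rule or sample size rests on OS. It does not dispose of it, because the next sentence of the plan commits to a formal test.

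**Matching may still be intended.** A one-sample log-rank test can use a matched or diagnosis-specific reference. A reader might infer that the plan has abandoned matching; the documents do not show that. They only leave it unspecified. The covariate adjustment for age, sex and prognostic factors in Section 14.0 belongs to the logistic models for response and does not cover OS.

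**MDS may be loose wording.** Section 11.1 speaks of an MDS response assessment for all participants. However, the primary endpoint definition in Section 14.0 itself lists MDS, MDS/MPN overlap and AML separately, so the literal reading is the likelier one.

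**The direction of bias is not known.** A reader might infer that the test is bound to show harm because AML was enrolled, or benefit because of TET2 selection. The documents support neither. They give no AML share and no AML survival, and their TET2 evidence concerns response (60% against 43%, and 82% against 45%), not survival. In the last table row the two biases roughly cancel.

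**Restricting to MDS could backfire.** This stands. If TET2 or calendar differences favour the trial group, removing AML removes an offset: false benefit goes from 2.4% pooled to 21% with 21 MDS patients. Nor is restriction a sure gain in power. That depends on AML survival being much worse than MDS survival.

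**Conclusion.** The inconsistency is in the text and should be corrected. A matched comparison for all treated patients is promised, and the only analysis specified uses an MDS cohort with no matching stated, although AML and blast-phase MPN patients are eligible and every patient is TET2-mutated.

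The size is conditional. At 25% AML, false worse findings rise from 3.6% to 5-8% if AML survival is only somewhat shorter than the reference, and to 17-32% if it is much shorter. In the other direction, an HR of 0.7 unrelated to treatment produces false benefit in 24% of trials of 28 MDS patients. All of this rests on the assumed AML share, AML medians, hazard ratios and alpha, on exponential survival, and on an external trial's median.

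The primary response decision is untouched. Some confounding would remain with any historical control; the diagnosis mismatch is the part that wording alone can remove.

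**What to change.** Amend the analysis plan in Section 14.0 in one of two ways, and bring Section 2.2 and the Protocol Summary into line.

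**(a) Keep a restricted test.** Compare only the trial's MDS patients with the historical cohort, adding MDS/MPN only if the cohort contains such patients. Report AML and blast-phase MPN survival by Kaplan-Meier without a test. Where the data exist, use TET2-mutated controls and a reference matched or standardised on one or two pre-specified variables, for example risk group and age. Otherwise delete the word matched and state that the cohort is not TET2-selected. State alpha and sidedness, label the comparison exploratory, and say that it cannot establish an effect of ascorbic acid.

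**(b) Drop the historical test** and report OS descriptively by diagnosis. This is simpler and fits the descriptive-statistics sentence already in the plan.

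**Cost.** Wording only, with no extra patients or visits. Under (a), matching or TET2 restriction needs cohort data that the documents do not confirm. At the 25-30% TET2 prevalence in MDS given in Section 1.1, 100 sequenced controls (an assumed number) would leave about 25-30.

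Precision also falls. If a two-sample HR were estimated against 100 controls at 0.39 deaths per patient, its 95% limits would be the estimate divided and multiplied by exp(1.96 × √(1/d₁ + 1/d₂)), where d₂ = 39.0. That factor is 1.96 for 28 trial patients (d₁ = 10.9), 2.12 for 21 (8.2) and 2.45 for 14 (5.47).

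Finally, (a) leaves any TET2 or calendar bias in place without the AML offset, so without TET2-matched controls a favourable result must not be read as a treatment effect.

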#### **3.1 Number of Subjects**

Approximately 28 patients will be enrolled in this trial.

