#### **6.5 Duration of Follow Up**

The clinical course of each adverse event will be followed until resolution, stabilization, or until it has been determined that the study treatment or participation is not the cause.

Serious adverse events that are still ongoing at the end of the study period will necessitate follow-up to determine the final outcome. Any serious adverse event that occurs after the study period and is considered to be possibly related to the study treatment or study participation will be recorded and reported immediately.

Following completion of active treatment (EOT) and while still on study (Follow up), patients will be followed for survival as of standard of care for up to 1 year. This follow up can either be done as a visit to the study doctor's clinic or via telephone call to the patient.

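### The overall-survival comparison treats an estimated historical curve as exact, so its standard error is too small by about √(1 + 28/m), where m, the cohort size, is not stated

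*Combined protocol and SAP*

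**What the plan says.** The analysis plan in Section 14 estimates overall survival by Kaplan-Meier and compares it with that of a "historical cohort of MDS patients treated at our institution with single agent Azacitidine between 2006-2012 using a one-sample log rank test". The secondary objectives (Section 2.2, and the Protocol Summary) describe the same reference as matched: "compared to matched historical cohort of patients treated with single agent Azacitidine". The endpoint is "Overall survival measured from start of treatment to death or last follow up".

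Section 3.1 sets the trial size: "Approximately 28 patients will be enrolled in this trial". On follow-up after treatment ends, Section 6.5 says that "patients will be followed for survival as of standard of care for up to 1 year".

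The documents do not give the number of historical patients or deaths, the matching ratio or variables, the significance level or sidedness of the test, or any allowance for the reference curve being an estimate. The same paragraph of Section 14 also says that secondary endpoints 1 to 3, which include overall survival, will be analysed descriptively.

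**The concern.** A one-sample log-rank test compares the deaths observed in the trial with the deaths expected under a reference hazard that is fixed in advance, as with a national life table. The reference here is a sample of the institution's own patients. Its survival curve has sampling error, so the expected number of deaths does too, and the test's variance has no term for it.

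This is separate from whether the cohort is comparable. A perfectly comparable cohort would still give a standard error that is too small. If matching works by discarding historical patients, better matching makes the problem larger because it shrinks the reference sample.

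At stake is the only planned survival comparison with azacitidine alone. In a single-arm trial, readers are likely to look to that result for what ascorbic acid adds.

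**Working it through.** The plan states no figure for this test, so there is none to reproduce. The check asks how often the planned test rejects when survival is truly the same in both groups.

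**Inputs**

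- Trial size n = 28 (Section 3.1).
- Historical cohort size m: not stated. Shown from 28 (what 1:1 matching would give) to 500.
- Level: not stated. Two-sided 5% assumed; one-sided 5% shown as an alternative.
- Survival: exponential with an 18-month median (assumed). This lies between the 15 and 24.5 months cited in Section 1.1, which were also tried.
- Trial follow-up: 12 to 30 months (assumed). For orientation, six 28-day cycles are 168 days, about 5.5 months; adding the 1 year in Section 6.5 gives about 17.5 months.

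**Formula**

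The test statistic is Z = (O − E)/√E, with O the observed and E the expected deaths. With a known reference, O − E has variance of about E. With a reference estimated from m patients with similar follow-up, E itself has variance of about E × n/m. The total is about E(1 + n/m), so Z has variance of about 1 + n/m instead of 1. The standard error is therefore understated by a factor of √(1 + 28/m), and the true two-sided level is

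2 × [1 − Φ(1.96/√(1 + 28/m))].

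**Results, nominal two-sided 5%, no true difference**

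The simulated columns estimate the reference cumulative hazard by Nelson-Aalen.

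| m | SE factor | 1.96/factor | True level, formula | True level, simulated | False-benefit tail, simulated (nominal 2.5%) |
|---|---|---|---|---|---|
| 28 | 1.414 | 1.386 | 16.6% | 16–18% | about 6% |
| 50 | 1.249 | 1.569 | 11.7% | about 12% | about 4% |
| 100 | 1.131 | 1.732 | 8.3% | 8.5–9% | about 3% |
| 200 | 1.068 | 1.836 | 6.6% | about 7% | not above 2.5% |
| 500 | 1.028 | 1.907 | 5.7% | about 6% | not above 2.5% |

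**Controls**

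- With the reference curve truly known, the one-sample test rejects 5.2% of the time, so the excess comes from estimating the reference.
- A two-sample log-rank test on the same data rejects about 5–5.5% of the time. With medians of 15 and 24.5 months and at least 18 months of follow-up, it stays between 4.7% and 5.7% for m from 28 to 500. Under those settings the one-sample test gives 17.2–17.9% at m = 28, 8.5–8.9% at 100 and 5.6–6.4% at 500.

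**Direction**

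Subtracting the false-benefit tail from the total leaves about 10–12% in the false-harm tail at m = 28 and about 5.5–6% at m = 100, against a nominal 2.5%. The asymmetry is already present with a known curve: in a one-sided 5% test the benefit direction rejects 3.8% and the harm direction 6.4%. With an estimated curve, a one-sided 5% test for benefit rejects 9.1% at m = 28, 6.7% at 56, 5.5% at 100, 4.8% at 200 and 4.1% at 500.

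**Is a small m plausible?**

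Section 1.1 puts TET2 mutations at 25–30% of MDS. If matching included TET2 status, which the plan does not say, an assumed 200 historical patients would supply 200 × 0.25 = 50 to 200 × 0.30 = 60. That falls near the 12% row.

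**The case against.** The strongest reply is that little rests on this p-value. Overall survival is secondary, Section 14 calls its analysis descriptive, and no level, power or decision rule is attached; the trial's decision rests on the response rate. This limits the severity. It does not remove the point, because the same paragraph names a formal test that will produce a p-value.

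The second reply is that the size depends on a cohort size that nobody outside the institution knows. This stands. A 2006–2012 institutional series could hold several hundred patients, and the two-sided level would then be about 6%. The 16–18% figure needs a reference of about 28, and no matching ratio is stated. Matching need not discard many patients either.

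The third concerns direction. A reader might infer that the trial would falsely claim a survival benefit 16% of the time. The calculations do not support that: most of the excess lies in the false-harm tail, and from about 200 historical patients the false-benefit rate is not above nominal.

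A reader might also infer that this is the trial's only comparative analysis. It is not. Section 14 also tests the response rate against 0.3 and plans comparisons of response by mutational status.

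Finally, a two-sample test holds its level only if the groups are exchangeable. Section 14 describes the reference as MDS patients, while the trial also enrols MDS/MPN overlap and AML, all with TET2 mutations. That is a separate problem, and a change of test does not solve it.

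**Conclusion.** The point holds, conditional on cohort size. The planned test omits the sampling error of the historical curve, nothing in the documents corrects for it, and the standard error is understated by about √(1 + 28/m): 41% too small a divisor at m = 28 (factor 1.41), 13% at 100 and 3% at 500. The consequence is material for a reference of up to about 100 patients and minor for several hundred.

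The formula assumes similar follow-up in the two groups. The simulated rates assume exponential survival, no true difference, and a two-sided 5% level that the plan does not itself set. They cover sampling error only and say nothing about comparability. The documents do not support a statement that the p-value is badly wrong whatever the cohort, nor that false claims of benefit are the main risk. This should be corrected before analysis, but it does not touch the primary endpoint.

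**What to change.** In the analysis plan of Section 14, replace the one-sample test with a two-sample log-rank test and a Cox hazard ratio with 95% confidence interval on the institution's patient-level data. Account for any matching or weighting (stratification by matched set, or robust variance), and use the same time zero in both groups. State the historical cohort size and number of deaths, and the level and sidedness of the test.

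Patient-level data are likely to be at hand, since the cohort was treated at the same institution and matching would need them, but the documents do not say so. If they cannot be used, either correct the one-sample variance for the estimated reference or report overall survival descriptively without a p-value.

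The cost is a short rewrite of Section 14, including the matching or weighting method that the plan does not yet define. It needs no new patients, visits or procedures. The downside is a wider interval, and any non-comparability of the cohort remains to be dealt with separately.
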